**NON-INTERVENTIONAL STUDY PROTOCOL
STUDY INFORMATION**

Title	Patient characteristics, treatment patterns and incidence of events (discontinuation, persistence, key primary clinical outcomes) in NVAF patients initiating OAC therapy in Colombia
Protocol number	B0661148
Protocol version identifier	1.0
Date of last version of protocol	10 October 2019
Active substance	Apixaban
Medicinal product	Eliquis
Research question and objectives	
Primary Objectives
 
• To assess demographic and clinical characteristics of NVAF patients treated with Oral Anticoagulants (OACs) in Colombia.• To describe treatment patterns (eg OAC usage, dose, concomitant medications, persistence) 
Exploratory Objectives
 
• To descriptively assess the time to clinical events (Effectiveness and Safety Outcomes) among patients persistent on OAC therapy 
Effectiveness outcomes: First stroke/ Systemic Embolism; CCI Safety outcomes: Major bleeding, CCI

Author	PPD

This document contains confidential information belonging to Pfizer. Except as otherwise agreed to in writing, by accepting or reviewing this document, you agree to hold this information in confidence and not copy or disclose it to others (except where required by applicable law) or use it for unauthorized purposes. In the event of any actual or suspected breach of this obligation, Pfizer must be promptly notified.

PFIZER CONFIDENTIAL

TABLE OF CONTENTS

LIST OF ABBREVIATIONS	5
1. RESPONSIBLE PARTIES.....	7
2. ABSTRACT	8
3. AMENDMENTS AND UPDATES	11
4. MILESTONES	12
5. RATIONALE AND BACKGROUND.....	13
6. RESEARCH QUESTION AND OBJECTIVES	14
7. RESEARCH METHODS.....	15
7.1. Study Design.....	15
7.2. Setting	16
Inclusion Criteria	17
Exclusion Criteria	17
7.2.3. Cohorts	17
7.3. Variables	18
Definition of outcome variables	23
7.4. Data Sources	44
7.4.1. Claim Database	44
7.4.2. Medical Record.....	44
7.5. Study Size	44
7.6. Data Management	44
7.6.1 Electronic Case Report (ECR).....	44
7.6.2 Record Retention	45
7.6.3 Patient Identification.....	46
7.6.4 Collection of Information	46
7.6.5 Database Retention	46
7.7 Data Analysis	46
7.7.1 Missing Data Management	47
7.8 Quality Control.....	47
7.9 Limitations of the research methods.....	47
7.10 Other aspects.....	48
8 PROTECTION OF STUDY SUBJECTS	48
8.1 Patient Information.....	48
8.2 Patient Consent.....	48
8.3 Institutional Review Board (IRB)/Independent Ethics Committee (IEC)	49
8.4 Ethical Conduct of the Study.....	49
9 MANAGEMENT AND REPORTING OF ADVERSE EVENTS/ADVERSE REACTIONS	50
10 PLANS FOR DISSEMINATING AND COMMUNICATING STUDY RESULTS	51
11. REFERENCES	52
12. LIST OF TABLES	53
13. LIST OF FIGURES	53
ANNEX 1. LIST OF STAND ALONE DOCUMENTS	53
ANNEX 2. ENCEPP CHECKLIST FOR STUDY PROTOCOLS	53

PFIZER CONFIDENTIAL

LIST OF ABBREVIATIONS

Abbreviation	Definition
ARB	Angiotensin II receptor blockers
ACE	Angiotensin-converting-enzyme inhibitor
AE	Adverse event
AEM	Adverse event monitoring
AIDS	Acquired Immune Deficiency Syndrome
AF	Atrial fibrillation
ANOVA	Analysis of variance
ATC	Anatomical Therapeutic Chemical
CHA ₂ DS ₂ -VASc	C: Congestive heart failure
	H: Hypertension
	A: Age \geq 75 years
	D: Diabetes mellitus
	S ₂ : Prior Stroke or transient ischemic attack or Thromboembolism
	V: Vascular disease (peripheral artery disease, myocardial infarction, aortic plaque)
	A: Age 65–74 years
	Sc: Sex category (female sex)
CHADS ₂	C: Congestive heart failure
	H: Hypertension
	A: Age \geq 75 years
	D: Diabetes mellitus
	S ₂ : Prior Stroke or transient ischemic attack or Thromboembolism
COPD	Chronic obstructive pulmonary disease
ECR	Electronic Case Report
GEP	Good Epidemiological Practice
GPP	Good Pharmacoepidemiology Practices
HAS-BLED	H: Hypertension
	A: Abnormal renal and liver function
	S: Stroke
	B: Bleeding
	L: Labile INR
	E: Elderly
	D: Drugs or alcohol
HMO	Health Maintenance Organizations
ICD-10	10th revision of the International classification of diseases
IEA	International Epidemiological Association
IEC	Independent Ethics Committee
INR	International normalized ratio
IRB	Institutional Review Board
ISPE	International Society for Pharmacoepidemiology
ISPOR	International Society for Pharmacoeconomics and Outcomes Research
MANOVA	Multivariate analysis of variance
NI	Non- interventional
NIS	Non-interventional study
NOAC	New oral anticoagulant
NSAID	Non-steroidal anti-inflammatory drugs
NVAF	Non-valvular atrial fibrillation

PFIZER CONFIDENTIAL

Apixaban
B0661148- NON-INTERVENTIONAL STUDY PROTOCOL
Final, 10 October 2019

Abbreviation	Definition
OAC	Oral anticoagulant
SAMe-TT ₂ R ₂	S: Sex (female)
	A: Age (<60 years)
	Me: Medical history
	T: Treatment
	T: Tobacco use (within 2 years)
	R: Race (non-Caucasian)
SPSS	Statistical Package for the Social Sciences
TIA	Transient ischaemic attack
VKA	Vitamin K Antagonist
VTE	Venous thromboembolism

PFIZER CONFIDENTIAL

2. ABSTRACT

Study title: Patient characteristics, treatment patterns and incidence of events (discontinuation, persistence, key primary clinical outcomes) in NVAF patients initiating OAC therapy in Colombia				
Protocol number	B0661148	Phase	4	Type
Condition/Disease	Non-valvular atrial fibrillation (NVAF)			
Number of patients	The total population of patients treated with OAC between January 1, 2013 and June 30, 2018 was analyzed in the claim dabtabase. For the purpose of the study, it contains the information of 7,500 patients, once they were verified that they met the inclusion criteria of the study.	Duration of the patients in the study	Follow-up will be performed until the patient presents a switch, discontinuation, death, event of stroke / systemic embolism or major bleeding, or until June 30, 2019.	
Country participants	Colombia	Duration of the study	8 months	
Rational and background: Non-valvular atrial fibrillation (NVAF) is an acute or chronic heart disorder that is associated with an increase in the mortality rate, strokes and other thromboembolic events (1). This is further increased by individual conditions of patients, such as hypertension, abnormal renal or hepatic function, stroke, history of or predisposition to bleeding, people over 65, among others. (2)				
One of the standard treatments for management of these patients is usually vitamin K antagonists (VKA, for example, warfarin); in the analysis of net clinical benefits of this therapy it is suggested that the effect of VKA is even more positive in patients with a high score on the HAS-BLED (hypertension, abnormal renal/liver function, stroke, bleeding history or predisposition, labile International Normalized Ratio, elderly, drugs/alcohol concomitantly) scale. (3) Another therapeutic alternative is the new oral anticoagulants (NOACs) — dabigatran, rivaroxaban and apixaban —, which according to evidence have advantages in efficacy and safety compared to warfarin (4) and even when the risk of bleeding and stroke are high, the net clinical benefit appears to be greater when compared to warfarin. (5) Likewise, there is a lower prevalence of intracranial hemorrhage and its different subtypes of patients being treated with new oral anticoagulants when compared to warfarin. (6)				
While it is true there are several studies that seek to understand the characteristics of patients who were diagnosed with NVAF under different treatment options, and even subpopulation analyses, the evidence at the national level is limited, both in demographic and clinical characteristics and in treatment patterns of this population. In a retrospective descriptive study of an emergency department in a third level care center in the city of Bogota, it was observed that the main comorbidities of patients with atrial fibrillation (AF) were arterial hypertension and heart failure where most patients do not receive anticoagulation. (7) In turn, for the overall population it is estimated that the prevalence of AF in Colombia (4.8%) seems to be higher than that reported in developed countries (0.03% to 1.25%) (8), according to a study conducted in a university hospital in the country (9).				
Taking into account the limited knowledge on the use of oral anticoagulants in patients diagnosed with NVAF in the country and, even more in the differences in the response to these therapies in different patient subpopulations. The purpose of this study is to assess the demographic and clinical characteristics, treatment patterns and incidence of events (discontinuation, persistence, key primary clinical outcomes) in NVAF patients that initiated OACs in study period.				
Primary Objectives				

 • To assess demographic and clinical characteristics of NVAF patients treated with oral anticoagulants (OACs) in Colombia. • To describe treatment patterns (eg OAC usage,dose, concomitant medications, persistence) 				

PFIZER CONFIDENTIAL

Apixaban

B0661148- NON-INTERVENTIONAL STUDY PROTOCOL

Final, 10 October 2019

Exploratory Objectives

- To descriptively assess the time to clinical events (Effectiveness and Safety Outcomes) among patients persistent on OAC therapy

Effectiveness outcomes: First Stroke/ Systemic Embolism; CCI

Safety outcomes: Major bleeding CCI

Design:

Observational, descriptive study of a retrospective cohort of adult patients diagnosed with NVAF in selected Health Maintenance Organizations (HMO) of Colombia. These patients will be identified from the drug claim database, whose index date of the study will be the first prescription with any of the oral anticoagulants, that is, they are patients with NVAF for the first time starting a therapy with any of the NOACs between January 1, 2013 and June 30, 2018 and follow up period will be among January 2013 to July 2019, to ensure that the last patients can provide follow-up for one year. Patients will be required to have an NVAF diagnosis before or on the index date and health plan for 6 months pre-index date (baseline period).

Population:

The total population of patients treated with any oral anticoagulant between January 1, 2013 and June 30, 2018 will be analyzed in the claim database. This means that patients who start warfarin and NOACs would be included within this period. Patients who initiate NOACs within the established period and who have been exposed to warfarin before 2013 will also be included.

Inclusion criteria:

Patients must meet the following inclusion criteria in order to be able to take part in the study:

- Patients with a diagnosis of AF considered according to the following diagnoses as per the 10th revision of the International classification of diseases (ICD-10) I48 codes at some point before or on the index date, without recorded valvular disease;
- Patients who have started treatment with apixaban, dabigatran, rivaroxaban and warfarin for the first time during the identification period, understanding as start of drug delivery by insurer, and after the diagnosis of AF between January 1, 2013 to June 30, 2018;
- Patients starting apixaban, dabigatran, rivaroxaban from January 1, 2013 to June 30, 2018 in patients previously exposed to warfarin;
- Patient had continuous health plan enrolment for 6 months pre-index date (baseline period);
- Patients older than 18 years old on the index date;
- NVAF diagnosis before or on the index date.

Exclusion criteria:

Patients who meet any of the following criteria will not be included in the study:

- Patients with any of the following diagnoses prior to the use of the treatments of interest or index date:
 - Valvular heart disease or valve replacement – ICD-10 codes: I05, I06, I07, I08, I09, I21, I22, I34, I35, I36, I37, I38, I39, I700, I702-I709; Q22, Q23, Q25, T82, Z95
 - Pregnancy during the study period. ICD-10 O00-O9A
 - Diagnosis of venous thromboembolism (VTE) – ICD-10 codes: I26, I80 - I82;
- Individuals with a transitory diagnosis of NVAF prior to the use of the treatments of interest or index date;
- Exposure to more than one OAC on or after the index date, during the follow-up period;
- NOAC doses different from those recommended by the manufacturing laboratories.

Data Collection:

PFIZER CONFIDENTIAL

The information will be analyzed in two moments: (i) the period of the index date, where the baseline information of patients will be collected; (ii) and the follow-up period, during this period the clinical results will be evaluated as well as the continuation of the treatment in the study population and for specific subpopulations.

Variables:

- Clinical and demographic characteristics
- Treatment patterns (OAC usage, dose, concomitant medications, persistence)

Effectiveness outcomes:

- First CCI switch of treatment, first event of stroke/ systemic embolism

Safety outcomes:

- Major bleeding

C
C

Data sources:

The information will be used in the study comes exclusively from secondary sources.

- Claim database:
 - The persistence on therapy and treatment patterns (duration of treatment, changes, persistence), pharmacy claim information, demographic information, diagnosis and insurance data.
- Medical records:
 - Baseline demographic and clinical characteristics and the information related to the outcomes of interest (stroke/systemic embolism, bleeding events and death)

Statistic analysis

This type of analysis is descriptive and explanatory, as it depends largely on the sample size. Continuous variables will be presented as means, standard deviation or other measures of central tendency or position, while categorical variables will be presented as frequencies and percentages.

Regarding bivariate analyses of continuous variables with normal behavior, the Student's t test will be performed. In case of presenting non-normal behavior, the Mann-Withney test will be used. For variables that are continuous with several categories, analysis of variance (ANOVA) will be assessed. In the event of presenting a non-normal behavior, the multivariate analysis of variance (MANOVA) test will be carried out. For categorical variables, the χ^2 test will be used.

The cumulative incidence of clinical outcomes (stroke/ systemic embolism and major bleeding) will be calculated throughout the study period, from which the incidence or survival curves will be derived using the Kaplan Meier method. Incidence of events will be explored in clinically relevant subgroups based on sample size.

A similar analysis will be performed for the group of patients who have not presented stroke/ systemic embolism or major bleeding events to estimate the time for discontinuation events and change of treatment.

In the independent variables, the significance will be analyzed, as a level of statistical significance $p < 0.05$.

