7.2. Setting

The study will be conducted with the Audifarma patient cohort that meets the inclusion and exclusion criteria between the periods from January 2013 to June 30, 2018. The follow up period will be among January 2013 to July 2019, to ensure that the last patients can provide follow-up for one year.

This study will include the entire population in which medical records can be accessed. This will depend on the authorization of the HMOs for review of medical records. Participating patients will be followed-up until the patient has a stroke/systemic embolism, major bleeding, discontinuation, change of treatment or until the data collection period is completed.

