7.2.3. Cohorts

After applying the inclusion and exclusion criteria, eligible patients will be assigned to the following four cohorts based on the OAC received on the index date.

1. Apixaban

2. Dabigatran

3. Rivaroxaban

4. Warfarin

Depending on the dosage of the NOAC prescribed on the index date, and in comparison to the standard conventions of total daily doses, patients may be classified into 3 different groups:

- **High doses:** apixaban 10 mg/day - rivaroxaban: 20 mg/day - dabigatran: 300 mg/day;
- **Low doses:** apixaban 5 mg/day - rivaroxaban: 15 mg/day - dabigatran: 220 mg/day
- **Other doses:** to be excluded, doses not recommended by the manufacturing laboratories.

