7.5. Study Size

The total population of patients treated with OAC between January 1, 2013 and June 30, 2018 was analyzed in the claim dabtabase. For the purpose of the study, it contains the information of 7,500 patients, once they were verified that they met the inclusion criteria of the study. This means that patients who start warfarin and NOACs would be included within this period. Patients who initiate NOACs within the established period and who have been exposed to warfarin before 2013 will also be included.

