7.7 Data Analysis

This type of analysis is descriptive and explanatory, as it depends largely on the sample size. Continuous variables will be presented as means, standard deviation or other measures of central tendency or position, while categorical variables will be presented as frequencies and percentages.

Regarding bivariate analyses of continuous variables with normal behavior, the Student's t test will be performed. In case of presenting non-normal behavior, the Mann-Withney test will be used. For variables that are continuous with several categories, analysis of variance (ANOVA) will be assessed. In the event of presenting a non-normal behavior, the multivariate analysis of

variance (MANOVA) test will be carried out. For categorical variables, the X² test will be used.

Exploratory analyses based on sample size:

The cumulative incidence of clinical outcomes (Stroke/ systemic embolism and major bleeding) will be calculated throughout the study period, from which the incidence or survival curves will be derived using the Kaplan Meier method. Incidence of events will be explored in clinically relevant subgroups based on sample size.

For the execution of the analysis, CCI and change of treatment, and missing treatments are considered as censures. Treatment comparison will be not conducted.

A similar analysis will be performed for the group of patients who have not presented stroke/ systemic embolism or major bleeding events to estimate the time for CCI change of treatment.

In the independent variables, the significance will be analyzed, as a level of statistical significance p < 0.05.

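### Student's t and classical ANOVA are named with no unequal-variance version; if group sizes and SDs both differ, the 5% level is not held, and Welch versions would avoid this at almost no cost

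*Combined protocol and SAP*

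**What the plan says.** The tests are set out in the Abstract (section 2, statistical analysis) and again in section 7.7.

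- Two groups: "Regarding bivariate analyses of continuous variables with normal behavior, the Student's t test will be performed". A rank test is named for non-normal data.
- More than two groups: "For variables that are continuous with several categories, analysis of variance (ANOVA) will be assessed".
- Threshold: "In the independent variables, the significance will be analyzed, as a level of statistical significance p < 0.05". Sidedness is not stated.

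Normality is the only property that decides between tests. Neither place mentions unequal variances.

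On group sizes, section 7.5 gives a total only: "it contains the information of 7,500 patients". Section 7.2.3 says "eligible patients will be assigned to the following four cohorts based on the OAC received on the index date", without a size for any cohort. Section 7.2 says "This study will include the entire population in which medical records can be accessed", so no group size is fixed by design. The plan does not say which groups the t tests and ANOVAs compare. In its exploratory outcome block, section 7.7 rules out treatment comparison; the Abstract does not carry that sentence.

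**The concern.** Student's t and classical ANOVA estimate one common variance from all groups, weighted by size. If one group is much larger, its variance dominates. The standard error is then too small when the smaller group is the more variable one, and too large when it is the less variable one. This depends on the groups' shares of the total and not on the total itself, so a database of thousands does not cure it.

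Imbalance is likely here. Nothing is allocated, and the yes/no characteristics in Table 1 include conditions such as AIDS, leukaemia and metastatic solid tumour, for which a near-even split is implausible. What is at stake is the meaning of the 0.05 label on comparisons of patient characteristics, which belong to the first primary objective. Some differences would be flagged too readily and others missed.

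**Working it through.** **Inputs from the documents.** Level 0.05 (section 7.7), taken as two-sided; total 7,500 (section 7.5). The total is a database count with no power, effect size, SD or group split behind it, so there is no sample-size calculation to reproduce.

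**Assumed inputs.** Share of the smaller group from 10% to 50%; SD ratio r (smaller group over larger group) from 0.67 to 2. The documents give neither.

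**Formula.** Let f₁ and f₂ be the group shares, with SDs s₁ and s₂. Up to a common factor 1/N,

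- true variance of the difference: V_true = s₁²/f₁ + s₂²/f₂
- variance assumed by Student's t: V_pooled = (f₁s₁² + f₂s₂²)(1/f₁ + 1/f₂)
- large-sample type I error: 2[1 − Φ(1.96 √(V_pooled/V_true))]

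**The stated level first.** If s₁ = s₂, the two variances are identical at every split and the error is 5.0%. If f₁ = f₂ = 0.5, both equal 2(s₁² + s₂²) and the error is again 5.0% whatever the SDs. Both conditions must fail for the level to move.

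**Worked at 20:80, larger group SD = 1**

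- r = 1.2: V_true = 1.44/0.2 + 1/0.8 = 8.45; V_pooled = (0.288 + 0.8) × 6.25 = 6.80; 1.96 × √(6.80/8.45) = 1.758; error 7.9%.
- r = 1.5: V_true = 12.5; V_pooled = 1.25 × 6.25 = 7.81; 1.96 × √0.625 = 1.549; error 12.1%.
- r = 0.8: V_true = 4.45; V_pooled = 0.928 × 6.25 = 5.80; 1.96 × √1.303 = 2.238; error 2.5%.

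**Range of true type I error, Student's t**

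| Split | r = 0.67 | 0.8 | 1 | 1.2 | 1.5 | 2 |
|---|---|---|---|---|---|---|
| 50:50 | 5.0% | 5.0% | 5.0% | 5.0% | 5.0% | 5.0% |
| 40:60 | 3.4% | 4.1% | 5.0% | 5.9% | 7.0% | 8.2% |
| 20:80 | 1.3% | 2.5% | 5.0% | 7.9% | 12.1% | 17.9% |
| 10:90 | 0.7% | 1.9% | 5.0% | 9.0% | 15.4% | 24.5% |

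**SD ratio at which the error is doubled or halved.** 10:90: about 1.25 or 0.84. 20:80: about 1.35 or 0.80. 25:75: about 1.44 or 0.76. 40:60: about 3.75 or 0.45.

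**Classical ANOVA, four groups, N = 7,500, simulated (200,000 runs).** The three smaller groups share one SD. With shares of 10/10/20/60%, the error is 2.2% at r = 0.8, 9.3% at 1.25 and 13.1% at 1.5. With four equal groups it runs from 5.0% to 6.4% for r from 0.5 to 2.

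**After the change.** In the same simulations Welch's t test (50:50, 20:80 and 10:90) and Welch's ANOVA stay between 4.9% and 5.1% in every scenario.

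**What the label change amounts to.** The smallest difference flagged at 0.05 is 1.96√(V/N), in SDs of the larger group. At 6,000/1,500 and r = 1.2: Student 1.96√(6.80/7,500) = 0.059, Welch 1.96√(8.45/7,500) = 0.066. At r = 1.5: 0.063 and 0.080.

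**The case against.** The strongest objection is that nothing in the documents shows harm. Several parts of it stand.

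- A reader might infer that the groups will be very unequal and that the error rate is therefore off by a factor of two or more. The documents do not support this. They give no cohort size or SD and do not name the groups compared. Unequal size alone does nothing. At 40:60, SD ratios from 0.5 to 2 give 2.7% to 8.2%, never a twofold error.
- A reader might infer that comparisons between anticoagulants are at risk. Section 7.7 says these will not be made. That sentence sits in the exploratory outcome block, so its reach to the baseline tables is arguable, but it cannot be ignored.
- A reader might infer that the primary objective is undermined. It is descriptive, and its summaries ("Continuous variables will be presented as means, standard deviation or other measures of central tendency or position") do not depend on the test. The worked examples show that the label changes only for differences of less than a tenth of an SD.
- The t test applies only to variables judged normal. Bounded integer scores such as CHA₂DS₂-VASc and HAS-BLED may go to the rank test instead.
- The plan does not use the words pooled or equal variances. Reading Student's t as the pooled test is natural, but it is a reading.

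What does not stand is that the point can be dropped. The tests are planned in two places and must compare some groups. The mechanism applies to any grouping, and no other provision covers it.

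**Conclusion.** The point holds in conditional form, as a free improvement and not as a demonstrated error. The plan names equal-variance tests for groups whose sizes nobody sets. Whether the 5% level is actually missed depends on group shares and SDs that the documents do not give. A modest SD difference at 20:80 moves the error to about 8%; doubling or halving needs a marked imbalance together with an SD ratio outside roughly 0.80 to 1.35 at that split, or 0.84 to 1.25 at 10:90. The figures assume two-sided testing and normal data. No confirmatory conclusion rests on these tests, so the priority is low.

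**What to change.** In the Abstract and in section 7.7, replace Student's t test with Welch's t test, and ANOVA with Welch's ANOVA, wherever means are compared between groups. Use them from the outset; do not add a preliminary variance test to choose between versions. State in the same sentence which groups are compared and that the tests are two-sided, if that is intended.

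The cost is a wording change in two places. The power loss is negligible at these sizes: with equal SDs and groups of 6,000 and 1,500, Welch's degrees of freedom are (1/1,500 + 1/6,000)² / [(1/1,500)²/1,499 + (1/6,000)²/5,999] ≈ 2,306 against 7,498 for Student's t, and both critical values round to 1.96.

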7.9 Limitations of the research methods

This study, as other observational studies, has some limitations; these are the result of the type of study and the source of information used. It is possible that there is some misclassification of the diagnoses of patients with NVAF as in turn in the diagnoses of the outcomes. For example, in the medical record, it is possible for the Investigator to use indirect information or to relate some type of approximation to obtain the variable or information of interest or to perform. Although this is a risk, the presence has been mitigated through a clear definition of the outcomes and with the case report format, which allows the Investigator to extract the relevant information only.

As for the claim database, a limitation is that prescription does not indicate whether the patient actually took the therapy as prescribed in both dosage and frequency.

On the other hand, this study will not obtain information related to hospitalizations of patients during the follow-up period; therefore, in the event of having any during this period it will not be known if the patient continued therapy. It is worth noting that these types of limitations are not differential among the cohorts of therapies to assess.

In spite of the limitations previously described, this information is very valuable, especially because it allows linking the claim information of medications with the medical records of each patient, providing a large sample size with a significant number of variables.

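### MANOVA is named as the fallback for non-normal data in more than two groups, but it is no remedy for non-normality; with one variable it is the ANOVA F test again

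*Combined protocol and SAP*

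**What the plan says.** The test-selection rule appears twice in nearly the same words, in the Abstract under Statistic analysis and in section 7.7 Data Analysis.

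- **Two groups, normal:** "Regarding bivariate analyses of continuous variables with normal behavior, the Student's t test will be performed".
- **Two groups, non-normal:** "In case of presenting non-normal behavior, the Mann-Withney test will be used".
- **Several categories:** "For variables that are continuous with several categories, analysis of variance (ANOVA) will be assessed".
- **Several categories, non-normal:** "In the event of presenting a non-normal behavior, the multivariate analysis of variance (MANOVA) test will be carried out". Section 7.7 repeats this. There the sentence begins "In the event of presenting a non-normal behavior, the multivariate analysis of" and runs over a page break to the same MANOVA ending.

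The List of Abbreviations expands MANOVA as multivariate analysis of variance, so it is not a local label for a rank method. Neither section offers a transformation, a permutation test, Kruskal-Wallis or any other option for non-normal data in more than two groups. The significance level is p < 0.05.

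The rule does not name its grouping factor. Section 7.2.3 says "eligible patients will be assigned to the following four cohorts based on the OAC received on the index date", and section 7.9 says that "these types of limitations are not differential among the cohorts of therapies to assess", which suggests the anticoagulant cohorts. The exploratory part of 7.7 states "Treatment comparison will be not conducted".

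**The concern.** A fallback for non-normality should either drop the normality assumption or depend on it less. MANOVA does neither. It extends ANOVA to several dependent variables at once and replaces normal errors with multivariate normal errors. There are two ways to read the rule, and neither helps:

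- **One dependent variable.** MANOVA is then algebraically the ANOVA F test, so the plan sets ANOVA aside and runs it again under another name.
- **Several dependent variables.** The hypothesis changes from a difference in one characteristic to a difference in a vector of characteristics. The plan never says which variables form that vector.

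An analyst therefore cannot both follow the text and deal with non-normality. The choice is between a step that does nothing and an unplanned departure from the protocol. What is at stake is the p-value attached to skewed continuous characteristics compared over more than two groups, such as the four cohorts or the five age bands in section 7.3.1.

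**Working it through.** The plan gives no figure to reproduce here. The check has two parts: whether one-variable MANOVA equals ANOVA, and how much the choice of test could matter.

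**1. Identity.** Let W be the within-group and B the between-group sum of squares, with N patients and k groups. For one dependent variable:

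- Wilks' lambda: Λ = W / (W + B)
- its F transform: F = [(1 − Λ)/Λ] × (N − k)/(k − 1) = [B/(k − 1)] / [W/(N − k)]

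The right-hand side is the one-way ANOVA F. On a simulated log-normal data set with four groups of 60, 40, 80 and 120 (N = 300):

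- Λ = 0.97324
- F = (0.02676/0.97324) × 296/3 = 2.713, p = 0.0451
- ANOVA computed directly: F = 2.713, p = 0.0451
- Kruskal-Wallis on the same data: H = 7.374, p = 0.0609

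In 700 further data sets (7,500 patients, four groups, seven distribution shapes), the Wilks, Pillai and Hotelling-Lawley p-values all matched ANOVA to within 1e-12. None of the 700 decisions at 0.05 differed.

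**2. Size of the effect.**

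Inputs:

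- Total of 7,500 patients: section 7.5.
- Level 0.05: section 7.7.
- Four groups: section 7.2.3.
- Assumed, because the documents give none: the split 833/833/1,667/4,167, the distribution shapes and the shifts.

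Each change was applied to one group of 833. For the log-normal shapes it was 0.1 log-SD: 0.02/0.2 = 0.03/0.3 = 0.10/1.0 = 0.15/1.5 = 0.1. Power rests on 4,000 data sets per row (Monte Carlo 95% half-width about 1.6 points). Disagreement rests on 1,500 (at most 2.5 points).

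| Shape and change | Power, F | Power, Kruskal-Wallis | Tests on different sides of 0.05 |
|---|---|---|---|
| Log-normal, log-SD 0.2 | 61.5% | 59.8% | 9.9% |
| Log-normal, log-SD 0.3 | 58.9% | 58.6% | 11.2% |
| 0–9 score, p 0.415 vs 0.400 | 52.8% | 51.5% | 5.8% |
| Age-like, left-skewed, +1.2 | 60.6% | 71.2% | 11.7% |
| Log-normal, log-SD 1.0 | 40.4% | 57.4% | 31.2% |
| Log-normal, log-SD 1.5 | 24.2% | 59.6% | 44.7% |
| Exponential, mean 1.1 vs 1.0 | 58.9% | 44.7% | 21.1% |

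With no true difference, rejection rates over the seven shapes were 4.6% to 5.6% for F and 4.5% to 5.1% for Kruskal-Wallis (half-width about 0.7 points).

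The last column depends heavily on the assumed shift. A separate run of 1,000 data sets per setting gave:

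| Log-SD | No shift | Shift as above | Larger shifts |
|---|---|---|---|
| 0.2 | 2.8% | 8.8% | 0.2% at exp(0.04) |
| 1.0 | 6.8% | 34% | 3.4% at exp(0.20); 0% at exp(0.30) |
| 1.5 | 8.0% | 50% | 27% at exp(0.30); 0.6% at exp(0.50) |

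The high disagreement rates therefore sit near the peak. They are not rates to expect in this study.

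**The case against.** The best defence is that almost nothing depends on this rule. The study is descriptive, no objective or sample size rests on an ANOVA p-value, and at several thousand patients the F test tolerates non-normality. Read as a one-variable test, the MANOVA sentence simply keeps ANOVA, which is defensible at this size and fits a plan that reports means. Most planned continuous variables (age, weight, height, BMI, the risk scores) are bounded or only mildly skewed, where the two tests perform about equally. Kruskal-Wallis is also not always stronger, as the exponential case shows.

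All of this stands as an argument about weight, and it is why the point is minor. It does not rescue the sentence, which presents MANOVA as the answer to non-normality.

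The reassurance also has limits. Section 7.5 ties the 7,500 to the inclusion criteria and does not mention the exclusions in 7.2.2. Section 7.2 makes inclusion depend on access to medical records, and 7.7.1 restricts analyses to observed cases. With small, very unequal groups (25/25/50/300) and log-SD 1.5, the F test's simulated type I error was 7.7%, against 4.5% for Kruskal-Wallis. Time since diagnosis is one planned variable that could be strongly skewed.

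The statement that treatments will not be compared does not make the rule moot. It appears under the exploratory outcome analyses, after the test-selection rule, and groupings other than treatment remain.

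**Conclusion.** The concern holds, and it is minor. That MANOVA is no remedy for non-normality, and equals ANOVA for one variable, is a mathematical fact that needs no assumption about the data. The error is in both places where the rule is stated, and it departs from the plan's own two-group logic.

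The consequence is confined to descriptive p-values for uncensored continuous characteristics in more than two groups. Means, standard deviations, frequencies and Kaplan-Meier estimates do not change. How often a conclusion would change depends on skew, cohort sizes and true differences, none of which the documents give. Under the assumptions shown, it is uncommon for mild skew or bounded scores and can be frequent only for strong skew with a small true difference.

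**What to change.** In the Abstract and in section 7.7, replace the MANOVA sentence with: *In the event of non-normal behavior, the Kruskal-Wallis test will be used.* This is the several-group counterpart of the Mann-Whitney rule already in the plan. Keeping ANOVA and deleting the fallback would also remove the error, but would leave the two-group and several-group rules inconsistent.

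As a clarification, name the grouping factor or factors to which the rule applies, and say whether baseline p-values across the four anticoagulant cohorts are intended, given the statement that treatments will not be compared.

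The cost is one sentence in two places and one clarifying phrase. Data collection does not change, and Kruskal-Wallis is available in the planned SPSS package. The small downside is that Kruskal-Wallis compares rank distributions rather than means, as Mann-Whitney already does for two groups.
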